7.5.1.3 Other Biomarkers of Exposure

The following BoExp will be measured in 24-hour urine collection samples as per the Schedule of Events (see also Appendix 1):

- Primary BoExp: MHBMA, 3-HPMA, S-PMA.
- Secondary BoExp: total NNAL, 1-NA, total 1-OHP, total NNN, 3-hydroxy(a)benzopyrene, 4-ABP, 2-NA, o-tol, NEQ, CEMA, HEMA, S-BMA, and HMPMA.

For normalization of BoExp, creatinine will also be measured in the 24-hour urine samples.

7.5.2 Other assessments

7.5.2.1 Risk markers

The following risk markers will be recorded/measured at the following time points:

Confidentiality statement: Data and information contained in this document are considered to constitute trade secrets and confidential commercial information, and the legal protections provided to such trade secrets and confidential information are hereby claimed under the provisions of applicable law. No part of this document may be publicly disclosed without the written consent of Philip Morris Products S.A.

- 8-epi-PGF₂ α to be measured in 24-hour urine on Day 0 and Day 5.
- 11-DTX-B2 to be measured in 24-hour urine on Day 0 and Day 5.

7.5.2.2 CYP1A2 activity test

CYP1A2 activity will be measured at Day 0, and at Day 5. Measurement of enzyme activity will be assessed through paraxanthine (PX) and caffeine (CAF) plasma molar concentrations approximately 6 hours (± 15 minutes) after the intake of one Tomerumin® (LionCorp.) caffeine tablet (around 170 mg caffeine) with 150 ml ± 10 ml water (Faber and Fuhr, 2004).

The exact time of intake of the caffeine tablet in the morning and of the blood sampling (blood sample will be taken 6 hours [± 15 minutes] after the intake of the caffeine tablet) must be recorded. Cytochrome P450 1A2 activity will be assessed by the measurement of the molar PX/CAF metabolic ratio (Faber and Fuhr, 2004).

7.5.2.3 CYP2A6 activity

CYP2A6 activity will be measured in plasma on Day 0, and at Day 6, using the metabolic molar ratio of *trans*-3'-hydroxycotinine/cotinine (Jacob et al., 2011). Blood sampling for CYP2A6 activity will be done prior to product use.

CYP2A6 activity drives the hepatic metabolism of nicotine to cotinine and subsequent metabolites.

7.5.2.4 Ames Mutagenicity Test

Urine mutagenicity, a biomarker for measuring mutagen load, will be measured on Day 0 and on Day 5 in 24-hour urine.

The urinary determination of each sample will be done in one bacterial strain (*S. typhimurium* strain YG1024), using S9 metabolic activation and 4 doses for each of the urine extracts.

7.6 Laboratory Assessments

7.6.1 Clinical Chemistry, Hematology, and Urine Analysis for Safety Panel

Hematology, clinical chemistry and urine analysis for the safety panel will be measured at Screening, Day 0, and at Day 6. Blood samples will be taken after at least 10 hours of fasting (see Section 6.6.2). The urine test will be performed semi-quantitatively as a urine dip-stick test. Parameters to be measured are listed in Table 3.

Table 3. Clinical Laboratory Parameters for Safety Panel

Hematology	Clinical Chemistry	Urine analysis
- Hematocrit	- Albumin	- pH
- Hemoglobin	- Total protein	- Bilirubin
- Mean corpuscular hemoglobin (MCH)	- Alkaline phosphatase (AP)	- Glucose
- Mean corpuscular hemoglobin concentration (MCHC)	- Alanine aminotransferase (ALT)	- Nitrite
- Mean corpuscular volume (MCV)	- Aspartate aminotransferase (AST)	- Red blood cell traces
- Platelet count	- Blood urea nitrogen (BUN)	- Protein
- Red blood cell (RBC) count	- Creatinine	- Specific gravity
- White blood cell (WBC) count	- Gamma-glutamyl transferase (GGT)	
- Differential WBC count:	- Fasting Glucose	
• Neutrophils	- Lactate dehydrogenase (LDH)	
• Basophils	- Potassium	
• Eosinophils	- Sodium	
• Lymphocytes	- Total bilirubin	
• Monocytes	- Direct bilirubin	
	- Total cholesterol	
	- Triglycerides	

7.6.2 Serology

A test for HbsAg, HCV, and anti-HIV1/2 and p24 antigen will be done at Screening. In case of positive results, the subject will be referred to appropriate medical care.

7.6.3 Urine Drug Screen

A urine drug screen will be performed at the study site at the Screening Visit and on the day of Admission (Day -2). The urine will be screened for amphetamines, barbiturates, benzodiazepines, cannabinoids, cocaine, and opiates.

Confidentiality statement: Data and information contained in this document are considered to constitute trade secrets and confidential commercial information, and the legal protections provided to such trade secrets and confidential information are hereby claimed under the provisions of applicable law. No part of this document may be publicly disclosed without the written consent of Philip Morris Products S.A.

7.6.4 Urine Cotinine Screening

A urine cotinine test will be performed at Screening and at Admission to the clinic (Day -2) in order to confirm the subject's smoking status. The test must detect cotinine with a cotinine threshold of ≥ 200 ng/mL.

7.6.5 Alcohol Breath Test

Subjects will have a breath alcohol test at the Screening Visit and at Admission to the clinic (Day -2) using an alcometer device.

7.6.6 Urine Pregnancy Testing

All female subjects will undergo pregnancy testing at the Screening Visit, at Admission (Day -2), at Day 6. Female subjects with a positive pregnancy test at the Screening Visit or at Day -2 cannot be enrolled and will be considered a screening failure. The product test at Admission must be done only in female subjects with a negative pregnancy test. In any case of a positive pregnancy test, the Investigator will inform the subject about the risks associated with smoking during pregnancy. In the event of an unclear urine pregnancy test, absence of pregnancy should be confirmed by a serum follicle stimulating hormone (FSH) level >20 IU/l.

All pregnancies detected during the study must be reported and handled as described in Section 8.5.

7.7 Sampling Handling and Storage

All blood samples are to be tested at a central laboratory with the exception of COHb blood sample and the safety laboratory panel which will be tested at a local laboratory (see Appendix 2). The urine cotinine test, urine pregnancy tests and urine drug screen will be done by personnel at the study sites.

Detailed procedures for sample collection and handling of samples are described in a separate Sample Handling Manual (SHM). Safety laboratory samples will be destroyed as per the laboratory's standard procedures. All other samples (except bio-banking samples)

Confidentiality statement: Data and information contained in this document are considered to constitute trade secrets and confidential commercial information, and the legal protections provided to such trade secrets and confidential information are hereby claimed under the provisions of applicable law. No part of this document may be publicly disclosed without the written consent of Philip Morris Products S.A.

will be destroyed after the CSR has been finalized. The facility(ies) at which the samples are stored will be informed in writing by the Sponsor when destruction of the samples will be allowed.

The bioanalytical lab(s) are listed in Appendix 2.

7.7.1 Blood samples

Blood samples will be collected by qualified and trained site personnel. Subjects should be in a seated position during blood collection. The maximal total volume of blood drawn for each subject will be around 170 ml, which includes 30 ml for safety and repeated analysis, 20 ml of blood for long-term storage of the bio-banking samples for further analysis of BoExp and risk markers and 10 ml for long-term storage bio-banking samples for transcriptomics (only if additional consents are given (see Section 7.7.3)).

The blood sampling for transcriptomics and the data related to these samples will be anonymized. Anonymized data and samples are initially single or double coded where the link between the subjects' identifiers and the unique code(s) is subsequently deleted. This is applicable for the blood bio-banking for transcriptomics only.

7.7.2 Urine samples

Spot urine samples will be used for the urine drug screen, urine cotinine screen, urine pregnancy tests, and safety urinalysis.

For the 24-hour urine collection, subjects will empty their bladders shortly before 06:30 AM on the study day indicated in the Schedule of Events (Appendix 1, Table A2). The collection period starts at 06:30 AM and ends on the following day at 06:29 AM. Shortly before 06:29 AM, after nearly 24-hours of urine collection, subjects will empty their bladder again and this urine will be used as the final portion of the 24-hour urine sample. During the sampling period, all urine passed must be collected and put into the sampling bottle, with the exception of about 10 ml for the spot urine tests (described above). No urine must be passed into the toilet. The start and the end time of the 24-hour urine collection will be recorded by the study site collaborator.

Confidentiality statement: Data and information contained in this document are considered to constitute trade secrets and confidential commercial information, and the legal protections provided to such trade secrets and confidential information are hereby claimed under the provisions of applicable law. No part of this document may be publicly disclosed without the written consent of Philip Morris Products S.A.

For assessment of urine BoExp, creatinine for normalization of urine BoExp, sample bio-banking and urine mutagenicity, aliquots from the 24-hour urine collection will be taken. In the Schedule of Events for the 24-hour urine collection (see Appendix 1, Table A2), the dot corresponds to the day on which the 24-hour urine collection period starts. For example, for NEQ measured at Day 5 in the 24-hour urine collection that starts on Day 5 and ends later on Day 6.

At time of Discharge on Day 6, subjects will empty their bladder shortly before 06:29 AM. This will be the last urine portion for the 24-hour urine for the Day 5 dot mark in the Schedule of Events.

7.7.3 Bio-banking Long Term Storage of Blood and Urine

If a subject gives consent for sample bio-banking for BoExp/risk markers, additional samples of urine (from the 24 hour urine collection) and serum/plasma (20 ml of blood total) will be collected.

- Samples from the 24-hour urine will be collected from the urine collections that started on Day 0, and on Day 5 respectively (10 tubes of 10 ml each per timepoint).
- Serum/plasma will be collected on Day 0, and plasma on Day 6 (2 tubes of 5 ml of blood drawn per timepoint. From one tube 2 x 1 ml plasma and from second 2 x 1 ml of serum will be collected and stored).

These samples are intended for possible later analysis of additional BoExp/risk markers. No genetic testing or pharmacogenomics testing will be performed on these samples.

If a subject gives consent for sample bio-banking of whole blood for transcriptomics, a total of 10 ml of blood will be collected to that purpose at Day 0 and Day 6 (1 tube of 5 ml per timepoint. The 5 ml will be further split into 2 tubes with 2.5 ml of whole blood each and stored).

The samples intended for sample bio-banking will be kept frozen according to the SHM, separate from the other samples collected, and will be shipped to a central storage facility.

After the final CSR is signed, samples of plasma/serum will be stored for a maximum of
Confidentiality statement: Data and information contained in this document are considered to constitute trade secrets and confidential commercial information, and the legal protections provided to such trade secrets and confidential information are hereby claimed under the provisions of applicable law. No part of this document may be publicly disclosed without the written consent of Philip Morris Products S.A.

5 years and samples of urine will be stored for a maximum of 2 years. The blood bio-banking for transcriptomics will be stored for a maximum of 5 years.

The facility at which the samples are stored will follow their procedures for destruction of banked samples if a subject withdraws their consent for sample bio-banking.

7.8 Other Study Procedures

7.8.1 Human Smoking Topography Assessment

Human smoking topography (HST) involves the measurement of each smoker's unique way of smoking CCs or using THS Tobacco Sticks using the HST SODIM[®] device. The HST SODIM[®] device, model SPA/M (SODIM[®] Instrumentation, Fleury les Aubrais, France) is a device which is used to measure smoking topography (see Appendix 5). It consists of a special cigarette holder (containing a constriction in the middle) which is placed between the smoker's mouth and the filter of the CC or the THS Tobacco Stick being smoked/used. The holder is connected by two narrow tubes to a portable data logger/recording system (see Appendix 5 for a description of the device). Any malfunction of the HST SODIM[®] device will be documented in appropriate log.

At Day 0, the HST SODIM[®] device has to be used for all CC smoked for all subjects. On Day 1 and Day 4 of the confinement period, the HST SODIM[®] device has to be used for every product use for all subjects in the CC and THS 2.2 arms.

Smoking topography with the HST SODIM[®] device will **not** be recorded for subjects smoking CC that are incompatible with the HST SODIM[®] device (e.g. slim CC).

For each subject, one HST SODIM[®] device will be assigned at Day -1, which will be used by that subject on all HST assessment days (in the case of malfunction, the device will be exchanged). SODIM[®] devices will be assigned to all subjects smoking non-slim CCs at each cohort but only the 40 first subjects will have an assigned HST SODIM[®].

From Day 1, for subjects in the SA arm, no HST assessments will be performed.

The Sponsor or designee will provide training on the use of the HST SODIM[®] device to the study site collaborator. The study site collaborator will, in turn, provide training to the subjects. All SODIM[®] devices will be returned to the Sponsor after completion of the study.

7.8.1.1 Human Smoking Topography Parameters:

The HST SODIM[®] device measures and records the flow and other per-puff parameters listed in Table 4 below. From the per-puff parameters (Table 4), the per cigarette parameters shown in Table 5 will be derived (representing average values or totals per cigarette).

Prior to calculation of the per-cigarette parameters, the Sponsor HST group will validate the data and discard any invalid data. Only valid data for the per-cigarette parameters will be part of the study database and will be analyzed.

Table 4. Human Smoking Topography – Per-Puff Parameters

Description	Variable	Unit
Puff number	Ni	
Puff volume	Vi	ml
Puff duration	Di	s
Average flow [Vi/Di]	Qmi	ml/s
Peak flow	Qci	ml/s
Inter puff interval	Ii	s
Sum of Ii and Di	DFi	s
Work [INT Pmi*FinalFlow*dt]	Wi	mJ
Average pressure drop	Pmi	mmWG
Peak pressure drop	Pci	mmWG
Average resistance [Pmi/Qmi]	Rmi	mmWG/ml/s
Peak resistance [Pci/Qci]	Rci	mmWG/ml/s

Table 5. Human Smoking Topography – Per-Cigarette Parameters

Description	Variable	Formula	Unit
Total number of puffs	NPC	$\sum Ni$	

Confidentiality statement: Data and information contained in this document are considered to constitute trade secrets and confidential commercial information, and the legal protections provided to such trade secrets and confidential information are hereby claimed under the provisions of applicable law. No part of this document may be publicly disclosed without the written consent of Philip Morris Products S.A.

Description	Variable	Formula	Unit
Total puff volume	TVOL	$\sum V_i$	ml
Average puff volume	AvgVi	$\sum V_i / \text{NPC}, i=1 \dots \text{NPC}$	ml
Average puff duration	AvgDi	$\sum D_i / \text{NPC}, i=1 \dots \text{NPC}$	s
Total puff duration	TDi	$\sum D_i$	s
Average flow	AvgQmi	$\sum Q_{mi} / \text{NPC}, i=1 \dots \text{NPC}$	ml/s
Peak flow	AvgQci	$\sum Q_{ci} / \text{NPC}, i=1 \dots \text{NPC}$	ml/s
Total inter puff interval	Tli	$\sum I_i$	s
Average inter puff interval	Avgli	$\sum Q_{ci} / \text{NPC}, i=1 \dots \text{NPC}$	s
Total smoking duration	TDFi	$\sum D_{Fi}$	s
Total Work	TWi	$\sum W_i$	mJ
Average Work	AvgWi	$\sum W_i / \text{NPC}, i=1 \dots \text{NPC}$	mJ
Average pressure drop	AvgPmi	$\sum P_{mi} / \text{NPC}, i=1 \dots \text{NPC}$	mmWg
Average Peak pressure drop	AvgPci	$\sum P_{ci} / \text{NPC}, i=1 \dots \text{NPC}$	mmWg
Smoking Intensity	SMINT	TVOL/TDFi	ml/s
Puffing Time Index	PTI	$(100 * \text{TDi}) / \text{TDFi}$	%
Puff Frequency	PF _{eq}	$\text{NPC} / (\text{TDFi} / 60)$	

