7.8.3.6 Human Smoking Topography Questionnaire

A specific questionnaire, used for exploratory purposes, has been developed by PMI to evaluate the impact of the utilization of the HST SODIM[®] device on smoker's smoking/inhalation experience in terms of ritual disruption.

This is a questionnaire with 5 items to be rated on a 5-point scale and open questions. Subjects will be asked by the Investigator to complete the HST questionnaire at:

Confidentiality statement: Data and information contained in this document are considered to constitute trade secrets and confidential commercial information, and the legal protections provided to such trade secrets and confidential information are hereby claimed under the provisions of applicable law. No part of this document may be publicly disclosed without the written consent of Philip Morris Products S.A.

-
- The end of the baseline period on Day 0 for all subjects smoking CC compatible with the HST device (i.e., non-slim CC).
 - On Day 4 for all subjects in the THS 2.2 and CC arms smoking CC compatible with the HST device (i.e., non-slim CC).

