9.2.3 Exposure Period (Days 1 to 5)

The tables in this Section show the assessments that will be performed during the confinement period (Day 1 to Day 5). Table 10 shows the assessments that will be performed on Day 1:

Table 10. Time Schedule – Day 1

Time	Blood sample	Procedures	Additional information
Start of procedure		Day 1	
		AE/SAE recording; concomitant medication	All day
		Support during smoking abstinence (SA arm only) if needed	All day
Before 06:30 AM		Subjects are informed of their assigned study arm.	
6:29 AM+/-20min		Analysis sample to be taken after final portion of urine has been added to Day 0 sampling bottle. Must be prior to first product use of Day 1	BoExp, creatinine, and Ames mutagenicity in 24-hour urine Risk markers: 8-epi-PGF2 α and 11- DTX-B2 Bio-banking for BoExp/ risk markers in 24-hour urine (if additional consent is obtained)

Confidentiality statement: Data and information contained in this document are considered to constitute trade secrets and confidential commercial information, and the legal protections provided to such trade secrets and confidential information are hereby claimed under the provisions of applicable law. No part of this document may be publicly disclosed without the written consent of Philip Morris Products S.A.

Time	Blood sample	Procedures	Additional information
Start of procedure		Day 1	
6:30 AM+/-20min		Start collection to Day 1 sampling bottle	
		Assessment of cough (VAS)	To be done prior to product use but not later than 10:00 AM
		MNWS questionnaire	To be done prior to product use but not later than 10:00 AM
		CO breath test	Within 15 minutes before first product use (for THS 2.2 and CC arms) or between 08:00 AM-09:30 AM (SA arm)
06:30 AM-11:00 PM		HST	In THS 2.2 and CC arms, HST SODIM [®] device has to be used for all product uses if compatible CCs are smoked
6:30 AM		Beginning of product use	
Before 10:00 AM		Breakfast	
10:00 AM-11:30 AM		Vital signs (blood pressure, pulse rate, respiratory rate)	At least 5 minutes in supine position prior to measurement
12:00 PM-01:30 PM		CO breath test	
Before 02:30 PM		Lunch	
04:00 PM-05:30 PM		CO breath test	
Afternoon		Snacks	
In the evening until 09:00 PM		Dinner	
08:00 PM-09:30 PM		CO breath test	
08:00 PM-09:30 PM	√	COHb in blood	
08:00 PM-09:30 PM	√	Nicotine, cotinine in plasma	
08:00 PM - 11:00 PM		MCEQ questionnaire (THS 2.2 and CC arms only), QSU-brief questionnaire	

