7.3.5 Human Smoking Topography Questionnaire

The HST questionnaire will be completed on Days 0 and 4 by all subjects smoking CC that are compatible with the HST SODIM[®] device (i.e., non-slim CC) to evaluate the impact of the use of the HST SODIM[®] device.

The HST questionnaire has 5 items rated on a 5-point Likert scale (strongly agree, agree, neither agree nor disagree, disagree and strongly disagree). The items are:

1. The smoking of the conventional cigarettes/products is different with the device.
2. You enjoy smoking with the device as much as without it.
3. The taste of the conventional cigarettes/products is different with the device.
4. The device is easy to use.
5. Your smoking is disturbed by the device.

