**Table 16: Assessment Windows**

Assessment	Nominal Time point(s)	Window
HST Questionnaire	Day 0	08:00 PM-09:30 PM
	Day 4 for all subjects in the THS 2.2 and CC arms smoking compatible CC	08:00 PM-08:30 PM
HST Recording	Day 0	06:30 AM-09:30 PM
	Day 1 and Day 4 for all subjects in the THS 2.2 and CC arms smoking compatible CC	06:30 AM-09:30 PM

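### The SAP closes the topography recording window 90 minutes before product use ends, and the protocol does not settle who gets a topography device, although every compatible smoker answers the device questionnaire

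*Protocol*

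**What the plan says.** **Recording window.** SAP Table 16 gives HST recording on Day 0, and on Days 1 and 4, as "06:30 AM-09:30 PM". The opening sentence of the same section (SAP 11.3) lets product use run from 06:30 AM to 11:00 PM. Protocol Table 10 (Day 1) puts "06:30 AM-11:00 PM" beside the HST row. Protocol Tables 9 and 13 (Days 0 and 4) ask for the device at all product uses and end smoking or product use at 11:00 PM. SAP Table 15 lists an HST recording outside its window as a minor deviation, and SAP 12.2 summarizes deviations by category and sub-category.

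**Who has a device.** Protocol 7.8.1 says that on Day 0 the "device has to be used for all CC smoked for all subjects", and that on Days 1 and 4 the "device has to be used for every product use for all subjects in the CC and THS 2.2 arms". The stated exception is incompatible cigarettes: topography is not "recorded for subjects smoking CC that are incompatible with the HST SODIM" device. The same section then assigns devices to "all subjects smoking non-slim CCs at each cohort but only the 40 first subjects will have an assigned HST" device. Neither document gives the number or size of cohorts, and the SAP does not mention the limit of 40.

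**Who answers the questionnaire.** Protocol 7.8.3.6 sets the first administration at "The end of the baseline period on Day 0 for all subjects smoking CC compatible with the HST device", and a second on Day 4 for compatible subjects in the THS 2.2 and CC arms. SAP 7.3.5 agrees: "The HST questionnaire will be completed on Days 0 and 4 by all subjects smoking CC that are compatible" with the device. SAP 12.6.3.3 tabulates the answers on the FAS. None of these sections makes having a device a condition.

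**The concern.** There are two separate drafting conflicts.

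First, a subject who follows the protocol and uses the device for a cigarette or Tobacco Stick at 10:00 PM produces a recording that the SAP calls out of window. The deviation summary would then count compliant behaviour alongside genuine timing errors, and the HST entry in that table would lose its meaning.

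Second, a requirement for all compatible subjects and a limit to the first 40 cannot both hold unless the limit never binds. A site cannot tell who needs a device, and a reader cannot tell the planned sample size for topography. The questionnaire exists to measure how the device disturbs smoking; its items ask about ease of handling, changed taste and disturbance. If some respondents never had a device, their answers carry no information on that question, yet they sit in the same percentages.

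**Working it through.** The documents state no sample size, power or precision for HST, so there is no figure of theirs to reproduce. The check is a comparison of clock times and a count of respondents under each reading of the limit.

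**1. Window**
- Product use, and HST in Protocol Table 10: 06:30 to 23:00 = 16.5 h.
- HST recording, SAP Table 16: 06:30 to 21:30 = 15.0 h.
- Gap: 16.5 - 15.0 = 1.5 h = 90 minutes. Share of the product-use day: 1.5/16.5 = 9.1%.

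This holds however the limit of 40 is read.

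**2. Questionnaire respondents without a device**

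Inputs: 160 subjects randomized 2:1:1 (80/40/40) and a limit of 40. The compatible share and the number of cohorts are not in the documents, so they are assumed and varied. Share without a device = 1 - (devices / compatible respondents).

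Limit of 40 overall, Day 0:

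| Compatible (assumed) | Respondents | Without a device |
|---|---|---|
| 100% | 160 | 1 - 40/160 = 75% |
| 90% | 144 | 1 - 40/144 = 72% |
| 50% | 80 | 1 - 40/80 = 50% |

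Day 4 gives the same shares. The SA arm drops out, leaving 120 respondents if all are compatible. About 40 x 3/4 = 30 of them are expected to have a device, and 1 - 30/120 = 75%.

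Limit of 40 per cohort, equal cohorts, all compatible:

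| Cohorts (assumed) | Cohort size | Without a device |
|---|---|---|
| 2 | 80 | 1 - 40/80 = 50% |
| 3 | 53.3 | 1 - 40/53.3 = 25% |
| 4 or more | 40 or fewer | 0% |

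**3. Topography parameters**

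Protocol 7.8.1 and SAP 7.4 derive per-cigarette parameters only from valid, processable device recordings. A subject without a device contributes nothing, so users and non-users are not mixed here. The cost is a smaller sample. In the extreme case (overall limit, all compatible, exact 2:1:1 among the first 40), THS 2.2 v CC has 20 v 10 subjects instead of 80 v 40. The standard error factor is sqrt(1/n1 + 1/n2):
- 80 v 40: sqrt(1/80 + 1/40) = 0.194 SD.
- 20 v 10: sqrt(1/20 + 1/10) = 0.387 SD.
- Ratio: 2.0.

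Under a per-cohort limit with four or more equal cohorts there is no loss.

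**The case against.** The strongest reply is that little depends on either slip.

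- **The limit may never bind.** The reference to each cohort stands in the same sentence as the number 40, so a per-cohort limit is at least as natural a reading as an overall one. With cohorts of 40 or fewer, every compatible subject has a device, and neither the questionnaire nor precision suffers. This stands. It is why the sizes are conditional and why 75% and the doubled standard error are extremes. It does not remove the contradiction, because cohort size is not stated.
- **The deviations are minor.** Per-protocol exclusion under SAP 10.2 and 11 turns on major deviations, and the SAP states no removal of late HST recordings from the analysis. SAP 12.2 also counts each subject once per category. This stands: no estimate changes. The number of deviations and the number of subjects flagged would still be wrong.
- **A reduced topography sample would be visible.** SAP 12.1.3 reports n and missing counts for continuous data. This also stands, but the questionnaire is categorical, and its table would not show who had a device.

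Two stronger readings are tempting. A reader might infer that the topography results themselves blend device users and non-users; they cannot, because only device recordings enter them. A reader might also turn the 9% gap into a share of subjects flagged. With 10 to 20 uses a day at independent, uniformly distributed times, 1 - (1 - 0.0909)^10 = 61% and 1 - (1 - 0.0909)^20 = 85%. The documents give no distribution of use over the day, and the figure could apply only to subjects with a device, so it is not a supported estimate for the study.

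**Conclusion.** Both conflicts are real and both are small.

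The window error needs no assumption: as written, any compliant HST recording between 09:30 PM and 11:00 PM, 9% of the product-use day, falls into a minor-deviation category.

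The assignment conflict is certain as text but conditional in effect. Depending on what 40 refers to, how many cohorts there are and how many subjects smoke compatible cigarettes, the share of questionnaire respondents without a device could lie anywhere from 0% to 75%. If the limit binds, topography rests on a smaller subset made up of the earliest subjects, with up to a doubling of the standard error for THS 2.2 v CC in the extreme case.

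The documents do not support reading this as a threat to the trial's conclusions. HST and its questionnaire are exploratory, the questionnaire analysis is counts and percentages only, and no primary or secondary endpoint uses either.

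**What to change.** - **SAP Table 16:** set the HST recording window to 06:30 AM to 11:00 PM on Days 0, 1 and 4, in line with SAP 11.3 and Protocol Table 10.
- **Protocol 7.8.1:** state one assignment rule, either all compatible subjects or the first 40, and if the latter, whether per cohort or overall. Bring the all-subjects sentences of that section into line with it.
- **SAP 7.3.5 and 12.6.3.3, with Protocol 7.8.3.6 to match:** restrict the HST questionnaire and its summary to subjects with an assigned device, and show n per arm. Devices are assigned subject by subject on Day -1, so this subset can be identified.

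No change to the topography model in SAP 12.6.3.2 is needed, since it already uses only device recordings. The cost is wording in two documents. No new devices or assessments are required.
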